### 6.2.1.2 Systemic contraceptives

Systemic contraceptives such as listed in Table 6-4 are not acceptable means of contraception (refer also to definition of acceptable effective contraception methods in Section 5.2), since these drugs may be ineffective due to decreased exposure in combination with QBW251 and result in contraceptive failure. These drugs may be taken for other indications (e.g. osteoporosis prophylaxis); the efficacy of the treatment may be impaired by low systemic availability, though, and should be monitored.

Table 6-4 Examples of contraceptives not recommended for systemic use as acceptable means of contraception as efficacy may be compromised by QBW251 administration

Medication	Period during which contraceptive effect may be compromised	Action taken
Drospirenone Ethinyl estradiol Etonogestrel Levonorgestrel Medroxyprogesterone acetate Norelgestromin Norethindrone Norgestimate Norgestrel	Use of these drugs is not prohibited, but in combination with QBW251 these may no longer constitute means of contraception, and thus their use does not fulfill the requirements of contraception stipulated in the exclusion criteria (risk of contraceptive failure). Patient is at risk to experience a pregnancy due to the interaction between systemic contraceptive and QBW251.	Pause study treatment and perform a urine pregnancy test. In order to resume study treatment, patient must have a negative urine pregnancy test and must use an approved contraception method (Section 5.2 – Exclusion #8). If urine pregnancy test is positive, refer to Section 9.1.1.

### 6.2.2 Prohibited medication

Use of the treatments displayed in the below table is NOT allowed after the onset of the prohibition period as indicated in Table 6-5 and Table 6-6. Should administration of one of these drugs during the course of the treatment period be required, study treatment should be discontinued.

Table 6-5 Prohibited medication

Rationale/Group	Medication 	Prohibition period				
Medication with a narrow therapeutic range and potential for increased exposure with QBW251 due to inhibition of CYP1A2	Theophyline Tizanidine	1 week prior to Day 1 until End of Study visit				
Medication with a narrow therapeutic range and potential for increased exposure with QBW251 due to inhibition of CYP2C19	Amitriptyline Clomipramine Imipramine	1 week prior to Day 1 until End of Study visit				
Medications lacking information on metabolizing enzymes	Pirbuterol	1 week prior to Day 1 until End of Study visit				
Strong uridine diphosphate glucuronosyl transferase (UGT) inhibitors, which will potentially increase systemic concentrations of QBW251	Mefenamic acid Probenecid Valproic acid	1 week prior to Day 1 until End of Study visit				

Rationale/Group	Medication 	Prohibition period					
Strong inducers mediating enzymes levels via PXR, which will potentially decrease systemic concentrations of QBW251	Valproic acid Apalutamide Avasimibe, Carbamazepine Enzalutamide Ivosidenib Lumacaftor Mitotane Phenytoin Rifampicin Rifapentine St. John's wort (Hypericum perforatum)	1 week prior to Day 1 until End of Study visit					
Any medication that may influence the response to treatment	Systemic or inhaled steroids (ICS alone), other systemic immunomodulators, recombinant human DNAse, any systemic or inhaled antibiotics, with the exception of oral macrolides mucolytics or hyperosmolar agents as noted in Table 6-2.	4 weeks prior to Day 1 until End of Study visit					

Table 6-6 Respiratory related medications and required washout periods

Prohibited respiratory-related medications ar	nd washout period prior to Day 1
Class of medication 	Minimum washout period prior to Day 1
Long-acting muscarinic antagonists (LAMA) (other than as ingredient of study maintenance therapy)	12 hours for twice-daily LAMAs 24 hours for once-daily LAMAs
Short-acting muscarinic antagonists (SAMA)	6 hours
Long-acting β 2 agonists (LABA)(other than as ingredient of study maintenance therapy)	12 hours for twice-daily LABAs, 24 hours for once-daily LABAs
Short-acting β 2 agonists (SABA) (other than trial rescue medication)	6 hours
Oral phosphodiesterase-IV inhibitor	7 days
Xanthines (any formulation)	7 days
Systemic corticosteroids	30 days
Inhaled corticosteroids (other than as ingredient of study maintenance therapy)	28 days
Intra-muscular depot corticosteroids	3 months

<sup>1 This table is not considered all-inclusive. Medications should be assessed for adherence to the indication and other inclusion/exclusion criteria. These medications are also prohibited if administered for other indications.

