As the completed thorough QT study (CQBW251A2105) indicated that QBW251 at 300 mg b.i.d. did not have clinically relevant effects on studied ECG parameters, single ECGs pre- and post-dose at Tmax will be performed at visits on Day 1, Day 28, Day 56 and Day 84 (end of treatment). These assessments will be complemented by PK sampling (trough and Cmax) on the matching timepoints, at visits on Day 1, Day 28, Day 56 and Day 84.

The morning dose on Day 84 will be the final dose administration for this treatment period. End of treatment assessment, e.g. safety assessment, lung function assessments and PROs will be performed on Day 84.

If spontaneous sputum collection is not possible at Day 84, site needs to reschedule the visit within 3 days after Day 84 and subject must continue to take study medication. If spontaneous sputum collection attempts are still not satisfactory, investigator may take decision to collect sputum sample after induction by the inhalation of saline. Other assessments that have been completed on Day 84 do not need to be repeated.

A second HRCT will be performed at Day 84 after the morning dose of study medication at site. If the HRCT can't be performed at Day 84 for any reason, the assessment needs to be planned within approximately the 3 coming days and patient must continue to take study medication.

In case of symptom deterioration (via e-diary alert), subjects must visit their study center to determine whether exacerbation criteria have been met and an immediate antibiotic treatment may be necessary. In addition, other markers of inflammation such as fibrinogen in blood will be taken to gain more information on systemic inflammation and sputum sample collection to determine if there are changes in pathogen or bacterial load that may have resulted in the exacerbation. Subjects experiencing an exacerbation during the treatment period will continue with the study treatment along with the standard of care (SOC) therapy for an exacerbation (i.e. antibiotics).

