### 6.2.3 Treatment for exacerbations and for bronchospasm

### **Pulmonary exacerbations:**

Treatment for pulmonary exacerbation (including systemic corticosteroids, antibiotics) is allowed. Use of treatment for pulmonary exacerbations must be recorded on the Concomitant medications/Significant non-drug therapies CRF.

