**AND** 

A clinician determines that a change in bronchiectasis treatment is required (e.g. requiring systemic glucocorticosteroid treatment and/or systemic or inhaled antibiotics).

A worsening of symptoms that either does not meet the above symptom definition but is treated by the investigator with antibiotics or steroids or both, or that meets the symptom definition but is not treated with antibiotics or steroids or both, is not considered a pulmonary exacerbation for the study.

For the above reported signs and symptoms, additional information will be collected to document if the reported signs and symptoms last for more than 48 hours.

Patients should contact the site when experiencing a pulmonary exacerbation. An unscheduled visit should occur within 2 working days of the event to confirm the diagnosis, unless the patient is hospitalized and thus unable to attend the site. AEs/SAEs, concomitant medications, and safety laboratory exams should be captured, as appropriate.

The start date for a pulmonary exacerbation recorded in the CRF should be the first day of treatment with antibiotics or steroids or both, as defined above. The end of a pulmonary exacerbation episode is marked by the end of treatment with antibiotics or steroids or both.

An exacerbation might result in missed or rescheduled visit(s) and missing associated CRF data in some circumstances.

Patients who develop a pulmonary exacerbation between screening and prior to treatment will be screen failed but will be permitted to be re-screened once the inclusion/exclusion criteria have been met (see Section 5.2 Exclusion criteria).

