# 9 Study discontinuation and completion

#### 9.1 Discontinuation

#### 9.1.1 Discontinuation of study treatment

Discontinuation of study treatment for a subject occurs when study treatment is stopped earlier than the protocol planned duration and can be initiated by either the subject or the investigator.

Subjects may voluntarily discontinue study treatment for any reason at any time.

The investigator must discontinue study treatment for a given subject if he/she believes that continuation would negatively impact the subject's well-being.

Study treatment must be discontinued under the following circumstances:

- Subject/guardian decision
- Pregnancy: a positive urine pregnancy test after start study drug requires immediate interruption of study drug until serum hCG is performed and found to be negative. If positive, the subject must discontinue study medication.
- Use of prohibited treatment outlined in Section 6.2.2.
- Any situation in which study participation might result in a safety risk to the subject.
- Following emergency unblinding
- Emergence of an AE reported as severe and suspected to be related to investigational drug or an SAE reported and suspected to be related to the investigational drug.

- Any laboratory abnormalities that in the judgment of the investigator, taking into consideration the subject's overall status, prevents the subject from continuing participation in the study.
- Any liver event requiring immediate discontinuation of study treatment, as specified in Table 16-2
- Individual serum creatinine increase ≥ 50% compared to baseline (must be confirmed).
   Please refer to Section 16.3 for discontinuation criteria due to emerging renal abnormalities.
- Study drug can be temporarily interrupted as a response to the occurrence of adverse events that do not fulfill the requirements above described for permanent discontinuation (refer to Section 6.5.1).

Discontinuation of study treatment will be at the discretion of the Investigator under the following circumstances:

- Any other protocol deviation that results in a significant risk to the subject's safety.
- Emergence of adverse event(s) or laboratory abnormalities that in the judgement of the Investigator, taking into account the subjects' overall status, prevent the subject from continuing participation in the study.

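### Protocol 6.2.2 and 9.1.1 stop study treatment when systemic corticosteroids are used, with no exception for exacerbations, although 6.2.3, 8.4.4 and 3.1 allow that therapy and continue study treatment

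*Protocol*

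**What the plan says.** **Stop side.** Protocol 6.2.2 bars the drugs in Tables 6-5 and 6-6 and then says: "Should administration of one of these drugs during the course of the treatment period be required, study treatment should be discontinued". The last row of Table 6-5 names "Systemic or inhaled steroids (ICS alone), other systemic immunomodulators, recombinant human DNAse, any systemic or inhaled antibiotics, with the exception of oral macrolides". It also exempts mucolytics and hyperosmolar agents by pointing to Table 6-2, and it runs from 4 weeks before Day 1 to the End of Study visit. Table 6-6 lists systemic corticosteroids again. Section 9.1.1 opens its mandatory list with "Study treatment must be discontinued under the following circumstances", and one bullet reads "Use of prohibited treatment outlined in Section 6.2.2". A separate list in 9.1.1 leaves some stops to the investigator's discretion; this trigger is not on that list.

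**Continue side.** Section 6.2.3 states: "Treatment for pulmonary exacerbation (including systemic corticosteroids, antibiotics) is allowed". Section 8.4.4 defines an exacerbation partly by a change in treatment, with the example "requiring systemic glucocorticosteroid treatment and/or systemic or inhaled antibiotics", and dates the episode by that therapy: "The end of a pulmonary exacerbation episode is marked by the end of treatment with antibiotics or steroids or both". Section 3.1, repeated in the protocol summary, states: "Subjects experiencing an exacerbation during the treatment period will continue with the study treatment along with the standard of care (SOC) therapy".

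**Analysis.** Protocol 12.4.3 leaves out CFU counts taken within 2 weeks after an exacerbation or around non-macrolide antibiotic use. It brings counts from later visits back in if the patient is then free of both. It also limits the primary analysis to data up to 1 day after the last randomized dose. SAP 6.1.3.1 keeps the rule on later visits.

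**The concern.** For a patient given systemic corticosteroids for an exacerbation, the protocol issues two opposite instructions. The drug is allowed and study treatment goes on; or the drug is prohibited and study treatment must end. The stop instruction is the more strongly worded, and it sits in the section a site would consult for discontinuation.

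Two things are at stake. A patient could lose study drug for receiving therapy that the protocol itself allows. And sites could read the rule differently, so that discontinuation, and the missing CFU counts that follow, would depend partly on the site's reading rather than on the patient's course.

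**Working it through.** The point rests on no figure in the plan, so the check is a comparison of sections followed by one patient traced through 12.4.3.

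**1. Does any text except steroids from the stop?**

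| Place | Antibiotics for an exacerbation | Systemic corticosteroids for an exacerbation |
|---|---|---|
| Table 6-5, last row | Listed; exception for oral macrolides only | Listed; no exception |
| Table 6-6 | Not listed | Listed; no exception |
| Table 6-2 | Allowed; action column asks for nothing | Not mentioned |
| 6.1.2 | Named as allowed | Not named |
| 6.2.3 | Allowed | Allowed |
| 8.4.4 | Qualifying treatment | Qualifying treatment |
| 3.1 | Continue; standard of care glossed as antibiotics | Continue, since the rule covers any subject with an exacerbation; steroids not named |
| 9.1.1 | Stop on use of a 6.2.2 drug; no exception | Stop on use of a 6.2.2 drug; no exception |

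For antibiotics, Table 6-2 supplies the missing exception, and the Table 6-5 row points to that table. For steroids, the only permission is in 6.2.3, and neither 6.2.2 nor 9.1.1 refers to it.

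**2. What happens to the CFU counts?** CFU is scheduled at Days 28, 56 and 84. Suppose one patient starts systemic steroids at Day 28. The course length is not in the documents; 7 to 14 days is assumed here only to trace the rule.

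- *Continue rule.* The episode ends with the course, and 2 more weeks are excluded: 28 + 7 + 14 = Day 49, to 28 + 14 + 14 = Day 56. The Day 84 count is kept. The Day 56 count is kept with the shorter course and is at the boundary with the longer one.
- *Stop rule, last dose Day 28.* The on-treatment window closes at 28 + 1 = Day 29. The Day 56 and Day 84 counts both fall outside it, although the rule on later visits would have kept at least the Day 84 count.

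The counts may also never be taken. Section 9.1.1 sends patients who stop to the End of Study assessments, and Table 8-1 shows no sputum bacterial load at that visit.

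**3. Can this be scaled to the trial?** No. That would need the exacerbation rate in this population, the share treated with systemic steroids, and the share of sites applying the stop literally. The documents give none of these. The 1.3 to 3 exacerbations per patient per year in 1.1 describe the disease in general. Entry here needs only one exacerbation since January 2019, plus stable pulmonary status.

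**The case against.** The best defence is that the protocol, read as a whole, already says continue. Section 6.2.3 follows directly after the prohibited-medication tables, deals specifically with exacerbations and names systemic corticosteroids. Section 6.2.1.1 lets the investigator treat an exacerbation as the investigator judges appropriate, and 6.6.2 asks for treatment to current recommendations or practice. A use expressly allowed in 6.2.3 can naturally be read as not prohibited, so the 9.1.1 bullet would not bite. In doubt, 6.2.1 sends the site to the sponsor.

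Much of this stands. The intended rule is very probably to continue, and contact with the sponsor lowers the chance of a wrong stop. But permission to give a drug does not by itself cancel a separate mandatory stop that carries no cross-reference to that permission. Contact with the sponsor leaves the outcome to whoever happens to ask.

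A second objection is that little now turns on it. The SAP records termination and drops the Bayesian model, the proof-of-concept criteria and the supplementary analyses. The 1-day window appears only in the protocol; SAP 6.1.3 speaks of all available data in the PD analysis set, and 6.1.3.1 does not restate the window. This also stands, and it limits the consequence. It does not remove the possibility that a patient was stopped under the literal rule while the study ran.

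**Conclusion.** The contradiction is real, sits in current operative text and is specific to systemic corticosteroids. Followed literally, the stop rule ends study treatment for permitted therapy and, under protocol 12.4.3, excludes later CFU counts that the section intends to use. The size is unknown. This conclusion rests on the wording alone, and the effect depends on sites having applied 9.1.1 as written.

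A reader might infer more, and the documents do not support it:

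- *That every treated exacerbation forces a stop.* Table 6-2 largely resolves the antibiotic case, and 3.1 and 6.1.2 point the same way.
- *That the trial was underpowered.* Any such figure would need an assumed steroid share, an assumed course length and universal literal stopping. The plan also allows for 16% drop-out and for up to 108 randomized. No power loss should be quoted, and nothing here puts the stated power in doubt.
- *That the primary estimand is wrong.* Its definition in 12.4.1 is unaffected; what is at risk is the data available to estimate it.
- *That the SAP analysis necessarily discards these counts.* The SAP does not restate the 1-day window.

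**What to change.** Add one exception to the stop sentence in 6.2.2, so that it covers both Table 6-5 and Table 6-6, and the same words to the 9.1.1 bullet: *except treatment of a pulmonary exacerbation allowed under Section 6.2.3 or antibiotics allowed under Table 6-2*. Placing it in the stop sentence avoids editing each table separately.

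Because the SAP records study termination, the practical step is retrospective. Cross-check the disposition and study-completion data against the concomitant-therapy listing, all already planned in SAP 7.2, and identify any patient who stopped study treatment because of exacerbation therapy. Report the number, including if it is zero.

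The cost is two short insertions by amendment or clarification letter, and a read-through of listings already planned. No new SAP output is needed, and there is no change to sample size, estimand, model or stated power.

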### 6.2.3 Treatment for exacerbations and for bronchospasm

### **Pulmonary exacerbations:**

Treatment for pulmonary exacerbation (including systemic corticosteroids, antibiotics) is allowed. Use of treatment for pulmonary exacerbations must be recorded on the Concomitant medications/Significant non-drug therapies CRF.

### **Bronchospasm:**

At screening and whenever needed thereafter, patients will be provided with a short acting beta agonist (salbutamol  $100~\mu g$  or albuterol  $90~\mu g$ ) inhaler to use as rescue medication on an "as needed" basis throughout the study. Nebulized salbutamol/albuterol is not allowed as rescue medication throughout the trial. The rescue medication will be supplied to the investigator sites locally by Novartis or provided by the study center and reimbursed by Novartis. No other rescue medication for bronchospasm is permitted.

The use of rescue medication (number of puffs taken in the previous 12 hours) will be recorded (once in the morning and once in the evening) by the patient, in the electronic Patient Diary. The rescue salbutamol/albuterol provided at screening for use during the study should not be recorded on the prior concomitant medication page of the eCRF.

### 6.2.4 Restriction for study subjects

For the duration of the study, subjects should be informed and reminded of the restrictions outlined in this section

### 6.2.4.1 Dietary restrictions and smoking

### **Dietary restrictions**

The following are the instructions for the investigational drug (QBW251/placebo):

• It is recommended not to take the investigational drug in together with high-fat meals (refer to SOM for details). The definition of high-fat meals follow the definition suggested by FDA in the draft guidance on Assessing the Effects of Food on Drugs in INDs and NDAs (FDA 2019): a meal containing at least 1000 kcal (4184 kJ), and at least 50% of that energy content from fat.

An example of a high fat meal would be for a total nutritional energy value of 1000 kcal:

- of which from proteins: 150 kcal
- of which from carbohydrates: 250 kcal
- of which from fats: 600 kcal.
- Patients can drink water as needed.
- Patients should be instructed not to take grapefruit, Seville oranges or their juice for 14 days prior to dosing, during treatment and until 7 days following the last dose as these products are considered as inhibitors of CYP3A.

### **Smoking**

Smoking is not prohibited during the study.

#### 6.2.4.2 Other restrictions

On study days when spirometry will be performed, patients should refrain from the following:

- Coffee, tea, chocolate, cola and other caffeine-containing beverages and foods and ice-cold beverage for 4 hours prior to spirometry
- Alcohol for 4 hours prior to spirometry
- Strenuous activity for 12 hours prior to spirometry
- Exposure to environmental smoke, dust or areas with strong odors

### 6.3 Subject numbering, treatment assignment, randomization

### 6.3.1 Subject numbering

The subject number assigned to a subject at screening remains the unique identifier for the subject throughout the study. For information on subject numbering, please see 'Subject numbering' section in the SOM.

### 6.3.2 Treatment assignment, randomization

Upon signing the informed consent form, the subject will be assigned the next sequential number by the investigator. The investigator or his/her staff will contact the IRT and provide the requested identifying information for the subject to register them into the IRT.

At Day 1, all eligible patients will be randomized via Interactive Response Technology (IRT) to one of the treatment arms.

The investigator or his/her delegate will contact the IRT after confirming that the patient fulfills all the inclusion/exclusion criteria. The IRT will assign a randomization number to the patient, which will be used to link the patient to a treatment arm and will specify a unique medication number for the first package of investigational treatment to be dispensed to the patient. The randomization number will not be communicated to the caller but will be used by the IRT system. The patient will retain the Subject Number throughout the study as the unique identifier. If the subject fails to be treated for any reason, the IRT should be notified within 2 days that the subject was not treated, and the reason will be entered into the CRF.

The randomization numbers will be generated using the following procedure to ensure that treatment assignment is unbiased and concealed from subjects and investigator staff. A subject randomization list will be produced by the IRT provider using a validated system that automates the random assignment of subject numbers to randomization numbers. These randomization numbers are linked to the different treatment arms, which in turn are linked to medication numbers. A separate medication list will be produced by or under the responsibility of Novartis Global Clinical Supply (GCS) using a validated system that automates the random assignment of medication numbers to packs containing the study treatment.

The randomization scheme for subjects will be reviewed and approved by a member of the Randomization Office.

Follow the details outlined in the SOM regarding the process and timing of treatment assignment and randomization of subjects.

Randomization will be stratified by macrolides use status and geographic region (from China/not from China).

